#### 10.1.1. Adverse Event Dictionary

Clinical and laboratory adverse events will be coded using the Medical Dictionary for Regulatory Activities (MedDRA minimum version 26.1). System Organ Class (SOC), High Level Group Term (HLGT), High Level Term (HLT), Preferred Term (PT), and Lower-Level Term (LLT) will be attached to the clinical database.

#### 10.1.2. Adverse Event Severity

Each AE will be assigned a “Grade” based on the Common Terminology Criteria for Adverse Events (CTCAE). Version 5.0 of the CTCAE will be used for this study. The severity grade of events for which the investigator did not record severity will be categorized

as “missing” for tabular summaries and data listings and will be considered the least severe for the purposes of sorting for data presentation.

#### **10.1.3. Relationship of Adverse Events to Study Drug**

The relationship of the Adverse Event to the study drug will be determined by the Principal Investigator, and assessed using the following definitions:

- **Related:** There is a distinct temporal relationship between the event onset and administration of the study drug. There is a known reaction to agent or chemical group or predicted by known pharmacology. The event cannot be explained by subject’s clinical state or other factors.
- **Unrelated:** Evidence exists that the AE has an etiology other than the study drug (e.g., pre-existing condition, underlying disease, intercurrent illness, or concomitant medication).

Events for which the investigator did not record relationship to study drug will be considered related to study drug for summaries, but data listings will show relationship as missing.

#### **10.1.4. Serious Adverse Events**

An SAE is an AE from this study that results in any of the following outcomes:

- Death
- Life-threatening situation (subject is at immediate risk of death).
- Inpatient hospitalization or prolongation of existing hospitalization.
- Persistent or significant disability/incapacity.
- Congenital anomaly/birth defect in the offspring of a subject who received study drug.

Important medical events that may not result in death, be immediately life-threatening, or require hospitalization, may be considered an SAE when, based upon appropriate medical judgment, they may jeopardize the subject *and* may require medical or surgical intervention to prevent one of the outcomes listed in this definition.

#### **10.1.5. Summaries of Adverse Events and Deaths**

Summaries (number and percent of subjects) of adverse events (by SOC, and PT) will be provided using the safety analysis set as follows:

- All treatment-emergent adverse events,
- All treatment-emergent treatment-related adverse events,

- All treatment-emergent treatment-related serious adverse events,
- All treatment-emergent adverse events that caused permanent discontinuation from study drug,
- All treatment-emergent adverse events leading to death.

A brief overall summary of TEAEs will show the number and percentage of subjects who had at least one of each of the above categories.

Multiple events will be counted once only per subject in each summary. For data presentation, SOC will be ordered alphabetically, with PT sorted by decreasing total frequency. For summaries by severity grade, the most severe event will be selected. In addition to the presentation by SOC, each summary will also be presented by preferred term only, ordered by decreasing frequency.

In addition to the summaries, data listings will be provided for the following:

- All treatment-related adverse events
- Serious adverse events
- Deaths
- Adverse events leading to discontinuation of study drug

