4. STUDY DRUG – VGT-309

VGT-309 will be administered over 15 to 20 minutes as an IV infusion. Following are details related to VGT-309 preparation, packaging and labeling and storage. Additional details will be supplied in the Pharmacy Manual.

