10. STATISTICS

The study analyses will be conducted in a GCP environment (ICH E6). All analyses will be pre-specified in a Statistical Analysis (SAP) and finalized prior to database lock. If the methods in the SAP do not agree with this protocol, the methods described in the SAP will govern the analysis.

Additional post-hoc statistical tests may be performed and will be further described in the SAP.

Quantitative data will be presented as a standard set of summary statistics (n, mean, standard deviation, median, minimum and maximum values). Categorical data will be expressed as frequency (%).

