10.4.1 Adverse Events

No statistical testing will be performed for safety data.

Adverse events will be summarized by the Medical Dictionary for Regulatory Activities (MedDRA) system organ class and preferred term. The MedDRA version current at the start of the study will be used throughout the study. A treatment-emergent adverse event (TEAE) is defined as any adverse event that begins on or after the date of administration of VGT-309.

An overall summary of TEAEs will be provided. The following summaries (number and percentage of subjects) of TEAEs (by System Organ Class and Preferred Term) will be provided:

- TEAEs.
- Treatment-related TEAEs.
- TEAEs leading to study drug discontinuation (infusion interruption or discontinuation)
- Serious TEAEs.
- Treatment-related Serious TEAEs.

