## 10. SAFETY ANALYSES

### 10.1. Adverse Events and Deaths

Adverse events will be summarized by the Medical Dictionary for Regulatory Activities (MedDRA) system organ class and preferred term. Events will be summarized on the basis of the date of onset for the event. Only treatment-emergent adverse events (TEAEs), defined as any adverse event that begins on or after the date of administration of VGT-309, will be collected and analyzed in this study. For purposes of this document, AEs refers to TEAEs.

An overall summary of TEAEs will be provided. The following summaries (number and percentage of subjects) of TEAEs (by System Organ Class and Preferred Term) will be provided:

- TEAEs
- Treatment-related TEAEs
- TEAEs leading to study drug discontinuation
- Serious TEAEs
- Treatment-related Serious TEAEs

All AEs collected during the study will be presented in a listing. Additionally, a listing will be provided for any AEs leading to death.

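### The category for adverse events leading to discontinuation is worded three ways, and the SAP 10.1.5 table leaves out infusion interruptions that Protocol 10.4.1 counts

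*SAP*

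**What the plan says.** Protocol 10.4.1 lists the TEAE summaries by system organ class and preferred term. One of them is "TEAEs leading to study drug discontinuation (infusion interruption or discontinuation"; the bracket makes interruption part of the category.

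SAP 10.1 repeats the protocol's list, but the entry reads only "TEAEs leading to study drug discontinuation", without the bracket. SAP 10.1.5 then specifies the tables again. Its entry is "All treatment-emergent adverse events that caused permanent discontinuation from study drug", and it says the brief overall summary of TEAEs will use the categories in that list. The listing named later in the same section is "Adverse events leading to discontinuation of study drug", without *permanent*. The protocol synopsis (Statistical Methods, Safety) also refers to study drug discontinuation with no mention of interruption.

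Protocol section 10 settles conflicts in the SAP's favour: "If the methods in the SAP do not agree with this protocol, the methods described in the SAP will govern the analysis". On dosing, Protocol section 4 states: "VGT-309 will be administered over 15 to 20 minutes as an IV infusion".

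**The concern.** Each subject receives one short infusion, so there is no later dose to withhold. An adverse event can affect dosing only by pausing the infusion or by ending it. The bracket in Protocol 10.4.1 covers both outcomes. The word *permanent* in SAP 10.1.5 covers only the second, and no readable SAP section names interruption at all.

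What is at stake is a tolerability count. If some infusions were paused for an adverse event and then completed, the SAP 10.1.5 row could read zero when the protocol's row would not. The reader of the overall summary would have no sign that an event had affected the infusion. The SAP also disagrees with itself, so two programmers working from SAP 10.1 and SAP 10.1.5 could produce different counts for what looks like the same table.

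**Working it through.** The plan states no figure to reproduce here, so the check is mainly a comparison of text.

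**1. Which events each place counts**

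| Place | Qualifier on discontinuation | Infusion ended for a TEAE | Infusion paused for a TEAE, then restarted |
|---|---|---|---|
| Protocol 10.4.1 | interruption included | counted | counted |
| Protocol synopsis | none | counted | not stated |
| SAP 10.1 | none | counted | not stated |
| SAP 10.1.5 listing | none | listed | not stated |
| SAP 10.1.5 table, and overall summary | permanent only | counted | not counted |

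The first and last rows cannot both be followed for a paused and restarted infusion.

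**2. Which one prevails.** Under Protocol section 10 the SAP governs where methods disagree. SAP 10.1.5 and Protocol 10.4.1 disagree, so the narrower category applies to the SAP 10.1.5 table. SAP 10.1 is silent on interruption. It neither contradicts the protocol's bracket nor restores it.

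**3. Where the event would still be seen.** It would be in the all-TEAE table and, if related, in the treatment-related table. It would also be in the full listing: "All AEs collected during the study will be presented in a listing". Only its identification as an event that affected the infusion would be lost.

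**4. Possible size.** The documents give no interruption rate. Assume n = 100 dosed subjects (the approximate enrolment target) and a rate r of TEAE-driven interruption followed by restart.

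- Expected number left out = n × r.
- Probability that at least one is left out = 1 − (1 − r)^n.

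| Assumed r | Expected number left out | Probability of at least one |
|---|---|---|
| 1% | 100 × 0.01 = 1 | 1 − 0.99^100 = 63% |
| 2% | 100 × 0.02 = 2 | 1 − 0.98^100 = 87% |
| 5% | 100 × 0.05 = 5 | 1 − 0.95^100 = 99% |

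These are illustrations of scale, not estimates for this agent. If no infusion is interrupted and restarted for a TEAE, all the definitions give the same count.

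**The case against.** The strongest reply is that the SAP can be read so that nothing is lost. SAP 10.1 promises its own table under the protocol's category name, without *permanent*. The precedence rule applies only to disagreement, and SAP 10.1 does not disagree with the bracket, so the protocol's meaning could carry over. The two SAP lists are also not substitutes for each other: SAP 10.1 includes all serious TEAEs, which the 10.1.5 table list omits, and 10.1.5 adds TEAEs leading to death. On that reading a broader table would sit beside a narrower one. The protocol is not uniform either, since its synopsis lacks the bracket.

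This stands as far as it goes. A reader might infer that the SAP removes interruption events from the safety report altogether, and the documents do not support that. The events stay in the all-TEAE tables and the adverse-event listing, and SAP 10.1 leaves room for the broader count. In addition, the detail of SAP 8.1.2 (exposure) and the table index in Appendix 1 are redacted. Interruptions may be tabulated there, and this cannot be checked.

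The reply does not remove the conflict. It asks the programmer to import a bracket that the SAP leaves out, and it does not change what the SAP 10.1.5 table and the overall summary would show.

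A reader might also link this to the Evaluable Population, because a subject whose paused infusion was completed could meet its 90% dose criterion. That has no bearing on this table: safety summaries use the safety population.

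**Conclusion.** The inconsistency is real and of low severity. There are three wordings for one category. The wording in the SAP 10.1.5 table, which feeds the overall TEAE summary, excludes interrupted and restarted infusions that Protocol 10.4.1 includes. Where that table is followed, the precedence rule makes the exclusion effective.

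The effect is confined to one descriptive safety category. No hypothesis test, error rate, power or sample size changes. The number of subjects affected is unknown: about 1, 2 or 5 at assumed rates of 1%, 2% or 5% in about 100 dosed subjects, and none if no such interruption occurs. The conclusion rests on the readable text and on interruption not being tabulated in the redacted parts. Even if it is tabulated there, the definitions in Protocol 10.4.1 and SAP 10.1.5 would still differ and need reconciling.

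**What to change.** Before database lock, use one definition in SAP 10.1, in the SAP 10.1.5 table and in the SAP 10.1.5 listing. It should match Protocol 10.4.1, so that TEAEs leading to either interruption or discontinuation of the infusion are counted. Interruption and permanent discontinuation could be shown as sub-rows under the combined count; this goes beyond what the protocol asks and is optional. If the narrower category is intended, the SAP should say so and justify it as a change from the protocol.

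The cost is a few words in three places, at most two extra table rows, and possibly a slightly higher count in the safety summary. One point needs confirming: the adverse-event details required by Protocol 9.2.1.2 include withdrawal from the study but do not name the effect on the infusion. The sponsor should check that the eCRF links an interruption to the event that caused it. The protocol's own table needs that link as well.

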## **10.2. Clinical Laboratory Evaluation**

Laboratory parameters (including clinical chemistry, hematology, urinalysis, coagulation) will be summarized using descriptive statistics at baseline and at each protocol-specified visit time points. Unscheduled visits will be listed. Changes from baseline will also be summarized. Clinically significant abnormal laboratory values will be reported as AEs.

All laboratory parameters and pregnancy test results will be provided in listings.

### **10.2.1. Summaries of Numeric Laboratory Results**

[REDACTED]	
[REDACTED]	
■	[REDACTED]
■	[REDACTED]
■	[REDACTED]

### **10.2.2. Shifts Relative to the Normal Range**

The following summaries (number and percentage of subjects) relative to the respective laboratory test normal ranges will be provided:

- Shift from baseline NCI-CTCAE grade to post-baseline grade at each post-baseline analysis window.

### **10.3. Vital Signs**

Vital signs will be summarized using descriptive statistics at baseline and at each protocol-specified visit time point. Unscheduled visits will be included in data listings. Changes from baseline will also be summarized.

All vital signs data will be provided in listings.

### **10.4. Physical Examination**

Physical Examination results will be listed.

### **10.5. Electrocardiogram**

All ECG results will be listed. Overall interpretation and percent change for each parameter from baseline will be summarized by time point.

[REDACTED]	
[REDACTED]	
■	[REDACTED]
■	[REDACTED]
■	[REDACTED]
■	[REDACTED]

### **10.6. Other Safety Measures**

The following safety measures collected will also be provided in listings:

- Pregnancy test results

## **12. SOFTWARE**

SAS Software Version 9.4. SAS Institute Inc., Cary, NC, USA.

### 13. APPENDICES

#### Appendix 1. Table of Contents for Statistical Tables, Figures, and Listings

The following TFL numbering is completed according to ICH guidelines. The ICH heading number and description are in **bold**. Minor changes from this planned index do not need to be amended in the SAP. Formal organization of tabulations may be changed during programming if appropriate, e.g., tables for the different variables may be combined into a single table, or tables with more than one variable may be split into several tables.

#### List of Tables

ICH Heading	Table Number	Table Description	Analysis Population
[REDACTED]		[REDACTED]	
	[REDACTED]	[REDACTED]	[REDACTED]
	[REDACTED]	[REDACTED]	[REDACTED]
		[REDACTED]	
	[REDACTED]	[REDACTED]	[REDACTED]
	[REDACTED]	[REDACTED]	[REDACTED]
	[REDACTED]	[REDACTED]	[REDACTED]
	[REDACTED]	[REDACTED]	[REDACTED]
	[REDACTED]	[REDACTED]	[REDACTED]
[REDACTED]		[REDACTED]	
	[REDACTED]	[REDACTED]	[REDACTED]
	[REDACTED]	[REDACTED]	[REDACTED]
		[REDACTED]	
	[REDACTED]	[REDACTED]	[REDACTED]
		[REDACTED]	
	[REDACTED]	[REDACTED]	[REDACTED]
	[REDACTED]	[REDACTED]	[REDACTED]
	[REDACTED]	[REDACTED]	[REDACTED]
	[REDACTED]	[REDACTED]	[REDACTED]
		[REDACTED]	
	[REDACTED]	[REDACTED]	[REDACTED]
[REDACTED]		[REDACTED]	
[REDACTED]		[REDACTED]	
	[REDACTED]	[REDACTED]	[REDACTED]
		[REDACTED]	
	[REDACTED]	[REDACTED]	[REDACTED]
		[REDACTED]	

[illegible]

[illegible]

██████████
